3.4 Mycobacterial Diseases

3.4.1 M. avium complex

Early in the course of the AIDS epidemic it was recognized that a nontuberculosis mycobacterium, M. avium complex, was isolated

frequently from patients with AIDS (37). Data from the Centers for Disease Control indicate that disseminated M. avium complex infection has been reported at the time of AIDS diagnosis in 4.5% of patients (9). Commonly the organism is isolated from blood and/or bone marrow (37). The lungs are involved less frequently (10), Autopsy series have suggested that as many as 53% of patients with AIDS have M. avium complex, usually isolated from multiple organs, at the time of death (38).

The infection is characterized histologically by huge numbers of organisms within involved tissues with there being little or no inflammatory response. This observation is perhaps a reflection of the fact that M. avium complex infection tends to be diagnosed late in the course of AIDS, when the immunosuppression is far advanced.

Data from Demopoulos and coworkers (39) suggest that M. avium complex infections do not influence the overall course of AIDS, at least in terms of median survival. However, these investigators found that there was an increased blood transfusion requirement in patients with disseminated M. avium complex.

The role of M. avium complex in causing lung disease in patients with AIDS is not clear. Although M. avium complex may be isolated from lung-derived specimens, the functional and prognostic implications of this have not been determined.

Treatment of M. avium complex infections is especially problematic even in nonimmunosuppressed hosts. In patients with AIDS a variety of drug regimens have been used but success has been infrequent (38). Most patients who have had M. avium isolated from blood have continued to be bacteremic and at autopsy multiple organs have contained organisms in spite of aggressive chemotherapy.

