to answer this question all HIV seropositive subjects (e.g., Groups A and B) will be included in the analysis. Possible predictor variables are HIV antibody status, stage of HIV infection, and HIV transmission category. Confounding variables are preventive treatment for infections, anti-HIV therapy, and immunosuppressive drugs. One of the principal outcome variables in this analysis will be presence or absence of P. carinii pneumonia. In order to calculate the prevalence of P. carinii pneumonia at, for example, 2 years into the study, a logistic regression model will be utilized which has the presence or absence of P. carinii pneumonia as the outcome variable and has the predictive and confounding variables as covariables. In this way, gross and adjusted odds ratios may be computed for the different subgroups of interest and the statistical equivalence of the magnitude of the gross or adjusted ratios may be assessed.

The second question in the primary objective concerns the association of various pulmonary diseases with subsequent morbidity and mortality. All seropositive subjects are to be part of this analysis and in this case P. carinii pneumonia will be one of the predictor variables. Confounding variables are transmission category, clinical and immunologic stage of HIV infection, and other coexisting diseases. One of the primary outcome variables for this analysis is mortality. In order to investigate the relationship of the presence or absence of P. carinii pneumonia on survival, a Cox regression model will be used in which mortality is the dependent variable and the presence or absence of P. carinii pneumonia is the predictive variable. The confounding variables above will appear as independent variables as well. In this analysis, comparisons will be made between the adjusted survival rates for those patients who developed P. carinii pneumonia versus those who do not over the course of the study.

Question 3 is, "What is the frequency with which multiple pulmonary diseases are present simultaneously and what are the common associations?" Again all HIV seropositive subjects will be used in this analysis and the major pulmonary diseases of interest will be P. carinii pneumonia, tuberculosis, mycobacterium avium complex infection, and cytomegalovirus infection. In order to discover associations which may exist among the different pulmonary diseases of interest, contingency

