Half-width 95% confidence interval for incidence of P. carinii pneumonia is 2% in Group A and 3% in Group B.

Question 2. What is the association of the following pulmonary diseases with subsequent morbidity and mortality: P. carinii pneumonia, tuberculosis, Mycobacterium avium complex infection, cytomegalovirus infection? Associations with subsequent morbidity and mortality will also be sought for less frequent processes including NIP, LIP, pyogenic bacterial infections, fungal infections and Kaposi's sarcoma involving the lungs. However, because of the infrequency of these processes, associations may be difficult to establish.

Groups studied

All HIV seropositive subjects

Predictive variables

Specific diseases as defined in Appendix 2

Confounding variables

HIV transmission category

Clinical and immunologic stage of HIV infection

Coexisting diseases

Diseases developing subsequently

Multiple pathogens present in the same patient

Outcome variables

Survival

Rate of change in pulmonary function

Days in hospital

Rate of weight loss

Rate of change in performance status

Evolution of chest film

Analysis

The analyses will be based on regression type models (linear, logistic, Cox regression) or multiple contingency table analysis models. Statistical measures studied will include differences in the rates (e.g., differences in the rates of specific abnormalities on chest films between those who had and those who did not have a specific pulmonary process) or means (e.g., days in hospital, rate of weight loss)

Question 3. What is the frequency with which multiple pulmonary diseases are present simultaneously and what are the common associations?

Groups studied

All HIV seropositive subjects

Predictive variables

Specific diseases (Appendix 2)

Confounding variables

HIV transmission category
Clinical and immunologic stage of HIV infection
Preventive therapy for infections

Outcome variables

Coexisting diseases

Analysis

The joint distributions of pulmonary diseases present at the same time in a patient will be analyzed using methods for categorical data. Significant associations among diseases will be described.

Question 4. What are the prevalence and incidence of specified symptoms, signs, radiographic findings, pulmonary function test abnormalities, laboratory findings, immunologic abnormalities and presence of indicators of HIV activity in patients with specific pulmonary diseases?

Groups studied

All HIV seropositive subjects

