Pneumocystis carinii pneumonia - Definite: Recovery of organisms on smear of lung derived specimens. Presumptive: The physician investigator must first review all available medical information and make a decision that a diagnosis of presumptive Pneumocystis carinii pneumonia is justified. First episode: The diagnosis of Pneumocystis carinii pneumonia (either definite or presumptive, as defined above) on the first such occasion. Episodes subject to first: the finding of P. carinii in any lung derived specimen, or the diagnosis of presumptive P. carinii pneumonia (as defined above) more than 2 months after completion of treatment for a previous episode and compatible clinical findings.

Tuberculosis - Pulmonary: Positive culture of lung derived specimen and an abnormality on chest x-ray or a compatible clinical picture. Extra pulmonary: Isolation of M. tuberculosis from any extra pulmonary source.

M. avium complex and other nontuberculous mycobacteria - Pulmonary: Isolation of M. avium or other nontuberculous mycobacteria from a lung-derived specimen in a patient with clinical illness who has no other pulmonary diseases identified. Extrapulmonary: Isolation of M. avium or other nontuberculous mycobacteria from an extrapulmonary source.

Cytomegalovirus Infection - Pulmonary: Demonstration of lung cell (including alveolar macrophage) infection by characteristic intranuclear and/or cytoplasmic inclusion bodies or by labelled specific DNA probes or monoclonal antibodies. Isolation of CMV from a respiratory specimen is desirable but optional for confirmation. Extrapulmonary: Demonstration of cell infection by characteristic intranuclear and/or cytoplasmic inclusion bodies. Isolation of CMV from blood.

Toxoplasmosis - Pulmonary: Histopathologic identification of T. gondii in lung tissue. Extrapulmonary: Histopathologic identification of T. gondii in extrapulmonary tissue. Diagnostic changes (2 fold in 3 weeks) in IgG titer or single IgM titer of 1:160 or higher. Of the brain: radiographic improvement after specific treatment for toxoplasmosis or recovery of organisms from brain tissue.

Pulmonary strongyloidiasis - Demonstration of larvae in any lung-derived specimen or demonstration of larvae in stool or duodenal aspirate and a clinical picture compatible with disseminated infection involving the lungs.

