If the participant dies while under the care of an attending physician from a hospital participating in the study, the autopsy will be performed at the hospital the next working day. Consent for autopsy will be obtained in the manner customary at the individual hospital and the standard hospital autopsy consent form will be used. Provided that there are no restrictions on the autopsy request form, a complete routine autopsy will be performed including gross examination and representative histologic sections of major organs including the heart, liver, spleen, bowel, kidney, enlarged lymph nodes, brain and eyes. Examination of the respiratory system will include at least five microscopic sections from trachea, lung, mediastinal and/or hilar lymph nodes, and any other area found to be of interest during the gross examination. Microscopic sections will be routinely stained with hematoxylin and eosin, gram, acid-fast and silver stains. Periodic and Schiff stains, Legionella DFA strains or probes, CMV probes or monoclonal antibody stains, and electron microscopy will be optional. If the autopsy is performed within 72 hours of death, mycobacterial, routine bacterial, fungal and viral cultures of pulmonary tissue will be submitted. The autopsy findings, microscopic and culture results, will be recorded on a standard Autopsy Form.

Appendix 6

TIME LINE - PHASE II

	11/1/88 - 10/31/89	11/1/89 - 10/31/90	11/1/90 - 10/31/91	11/1/91 - 10/31/92
A) Recruitment				
B) Patient Interview & Exams				
1) Initial Visits				
2) Follow-up Visits				
3) Symptom Visits				
C) Diagnostic Procedures (CXR, PFT, Sputum Induc)				
D) Laboratory Tests				
E) Serum Bank				
F) Autopsies				
G) Recruitment Reports				
H) Yearly Progress Reports				
I) Data Collection & Entry				
J) Quality Control				

Appendix 8

Serum Tracking and Shipment Proposal

For the Pulmonary Aids Clinical Study, serum should be collected at the initial visit, all follow-up visits, and during certain symptom generated visits. Symptom generated visits that require serum to be collected are those in which additional evaluation is required because of chest radiographic abnormalities, reduced DLCO values or abnormal GA scans.

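### Several Appendix 2 case definitions can be met by autopsy tissue alone, so exposure in Question 2 can depend on death and case-finding in Questions 1, 6 and 7 varies with death and autopsy rates

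*Protocol*

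**What the plan says.** **Autopsy data.** Appendix 5 (Autopsy Procedures) plans at least five microscopic sections from the respiratory system, with hematoxylin-eosin, Gram, acid-fast and silver stains. If the autopsy is within 72 hours of death, lung is also cultured for mycobacteria, bacteria, fungi and viruses. "The autopsy findings, microscopic and culture results, will be recorded on a standard Autopsy Form". Autopsy depends on death under the care of a participating hospital's physician, and on consent. Section 10.2.6 sends all fixed tissue to a pathology panel whose consensus changes the data records, with no exception for autopsy tissue.

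**Case definitions met by a specimen or tissue alone.** Pulmonary cytomegalovirus infection is "Demonstration of lung cell (including alveolar macrophage) infection by characteristic" inclusion bodies, or by probes or antibodies, with no clinical condition. Toxoplasmosis, candidiasis, histoplasmosis/coccidioidomycosis, herpes simplex, nocardiosis, lymphoid and nonspecific interstitial pneumonitis, Kaposi's sarcoma and lymphoma can likewise be met by lung tissue or a lung-derived specimen. Definite first-episode P. carinii pneumonia is "Recovery of organisms on smear of lung derived specimens". The word smear makes it arguable whether autopsy sections qualify.

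**Case definitions that ask for more.** Pulmonary tuberculosis is "Positive culture of lung derived specimen and an abnormality on chest x-ray or a compatible clinical picture". Pulmonary M. avium complex is isolation "from a lung-derived specimen in a patient with clinical illness who has no other pulmonary diseases identified". Cryptococcosis and aerobic bacterial pneumonia need a compatible clinical setting, and repeat P. carinii pneumonia needs compatible clinical findings.

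**Use in the analysis.** The Question 1 outcome is the Appendix 2 diagnoses. The Question 2 predictor is "Specific diseases as defined in Appendix 2", with survival among the outcomes. Section 9 describes a Cox model that compares "adjusted survival rates for those patients who developed P. carinii pneumonia versus those who do not over the course of the study". No text says whether a diagnosis made only at autopsy counts.

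**The concern.** A diagnosis first made at autopsy can occur only in someone who has died. If it counts as a case in Question 2, it enters the diseased group as a death by construction, while survivors with the same silent disease stay in the comparison group. Cytomegalovirus shows what is at stake. Section 3.7 calls its role in lung disease poorly defined and says that it does not seem to alter the course of P. carinii pneumonia. An incidental finding at autopsy would still be tied to death.

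The second problem is unequal ascertainment. Autopsy finds real disease, but it looks only in those who die and are autopsied. Group B is expected to lose far more subjects than Group A, and consent practice and place of death will differ between centers. Differences between groups (Question 1), transmission categories (Question 6) and centers (Question 7) would then partly reflect who was examined after death. Co-occurrence (Question 3) inherits the same selective search.

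**Working it through.** **Inputs from the protocol.** Analyzed subjects: 527 in A and 527 in B (Table 5B). Three-year mortality: 15% in A, 50% in B (footnote to the mortality tables, Appendix 3). One-year P. carinii pneumonia frequency: 5% and 20% (footnote to Table 3.3).

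**Assumed, because the protocol gives neither.** f = share of deaths autopsied, 10–50%. q = share of autopsied deaths with the disease first found then, 5–50%.

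**1. The plan's own precision.** Half-width = 1.96·√[p(1−p)/n].
- A: 1.96·√(0.05·0.95/527) = 1.86%, stated as 2%.
- B: 1.96·√(0.20·0.80/527) = 3.42%, stated as 3%.

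Both reproduce.

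**2. Frequency added by autopsy-only cases.** Added frequency = m·f·q, with m the three-year mortality.

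| f, q | Group A | Group B |
|---|---|---|
| 10%, 5% | 0.08 points | 0.25 points |
| 30%, 20% | 0.15·0.30·0.20 = 0.90 points | 0.50·0.30·0.20 = 3.00 points |
| 50%, 50% | 3.75 points | 12.5 points |

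At equal f and q, B gains 0.50/0.15 = 3.3 times as many cases per subject as A. The half-widths in step 1 are a yardstick only: they refer to one-year P. carinii pneumonia, while these additions build up over three years.

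**3. Mortality comparison, developed versus did not develop.** Assume a disease with no effect on death, diagnosed in life in 5%, with constant low onset and a constant death hazard. Pooled mortality is (15% + 50%)/2 = 32.5%, so the cumulative hazard is H = −ln(0.675) = 0.393.
- Mortality of those diagnosed in life: 1 − H(1−m)/m = 1 − 0.393·0.675/0.325 = 0.184.
- Mortality of the rest: (0.325 − 0.05·0.184)/0.95 = 0.332.
- Ratio with no autopsy cases: 0.184/0.332 = 0.55. The same steps give 0.51 at 15% mortality and 0.60 at 50%.

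The ratio is below 1 because a subject must live long enough to be diagnosed.

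Now move autopsy-only cases. Deaths diagnosed in life are 0.05·0.184 = 0.00918 of the cohort, and the other deaths are 0.325 − 0.00918 = 0.31582. Moved = 0.31582·f·q. At f = 30%, q = 20% this is 0.01895, and the ratio is

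[(0.00918 + 0.01895)/(0.05 + 0.01895)] / [(0.31582 − 0.01895)/(0.95 − 0.01895)] = 0.408/0.319 = 1.28.

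| Yield q | f = 10% | f = 30% | f = 50% |
|---|---|---|---|
| 10% | 0.70 | 0.96 | 1.18 |
| 20% | 0.84 | 1.28 | 1.61 |

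Two biases of opposite sign are mixed, and the net can fall on either side of 1.

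**4. Disease dated at diagnosis.** If disease is a time-dependent covariate dated at diagnosis in life, the ratio in this example is 1. If autopsy-only cases are also counted as exposed at death, each adds a death to the exposed group and no follow-up time. The rate ratio is then [(0.00918 + moved)/0.00918] / [(0.31582 − moved)/0.31582].
- f = 10%, q = 10%: moved 0.00316, ratio 1.344/0.99 = 1.36.
- f = 50%, q = 20%: moved 0.03158, ratio 4.44/0.90 = 4.9.

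The distortion shrinks for diseases often diagnosed in life, because more exposed deaths are already counted.

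**The case against.** The strongest reply is that counting autopsy findings as cases is an inference from silence. Findings go on their own form, and Question 2 asks about morbidity and mortality that follow the disease. Its other outcomes, such as weight loss and change in lung function, need survival after diagnosis. How to code such cases could sit in an analysis plan that is not at hand. This limits the point but does not remove it. The protocol itself fixes the case definitions and the comparison, and neither carries the idea of subsequent death into a rule.

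It is also fair that autopsy finds real disease and that the primary objective is to describe which lung diseases occur. Leaving autopsy-proven cases out of the rates loses information. In Question 2, a fatal pneumonia not recognised in life would be treated as a death without that disease. That is why a sensitivity analysis belongs with the fix.

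Two stronger readings are tempting. A reader might infer that a harmless disease will necessarily appear lethal. Step 3 does not support this: with no autopsy cases the crude comparison is biased downward, and at modest yields the net ratio stays near or below 1. A reader might also size the problem from Section 3.4.1, where "as many as 53% of patients with AIDS have M. avium" complex at the time of death. That figure counts any organ and is not limited to disease unknown in life. The same section says the lungs are involved less often, and the pulmonary definition of M. avium complex is among the stricter ones. It is not an autopsy-only lung yield.

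**Conclusion.** The point holds for diagnoses that Appendix 2 defines by lung tissue or a lung specimen alone: most clearly cytomegalovirus, the others listed above, and arguably first-episode P. carinii pneumonia. It does not hold for Appendix 2 as a whole. Where clinical or x-ray findings are required the problem is narrower, though a dying patient may often meet them.

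The size cannot be fixed from the protocol. Over the assumed ranges the added frequency runs from negligible to well beyond the stated precision. At 30% autopsy and 20% yield it is 0.9 points in A and 3.0 in B. In Question 2 the defect is that exposure depends on the outcome; the direction of the net error is not determined. Excluding autopsy-only cases restores a ratio of 1 for a harmless disease only if disease is also dated at diagnosis in life. Without that dating, step 3 leaves a ratio of about 0.5 to 0.6. These ratios rest on constant hazards and 5% diagnosed in life.

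**What to change.** 1. **Appendix 2:** flag any diagnosis first established at autopsy as autopsy-only.
2. **Section 9 and Appendix 1, Question 2:** do not use autopsy-only diagnoses as predictors of survival. Enter disease as a time-dependent covariate dated at diagnosis in life.
3. **Questions 1, 3, 6 and 7:** for group and center comparisons, base the main rates and co-occurrence tables on diagnoses made in life. Report autopsy-only diagnoses separately, with the number autopsied as denominator by group and center. Add a sensitivity analysis that includes them.

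The cost is a few sentences and one flag derived from the existing Autopsy Form. No data are discarded. The downside is fewer counted cases of rare, tissue-only diseases in the main tables, which the separate report and the sensitivity analysis partly offset.

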It is very important that the serum storage box be labeled in the same manner as the serum storage log. This will help ensure that mistakes are not made when serum addresses in the particular cells of the serum storage box are recorded on the serum storage log. Any writing done on the serum storage box or on the cryotube labels should be done using a specialized freezer pen.

To label the serum storage box, remove the top from the serum storage box and set it aside. All labeling of the serum storage box will be done on the sides of the box and not the lid of the box. To begin, label one of the sides as FRONT (Figure 1). This will act as a reference point to keep the orientation of the box the same during form

completion. On the side that you labeled FRONT, number the columns of the grid from 1 to 9 starting in the left corner of the box and proceeding to the right (Figure 2). With the FRONT side of the box still facing you, locate the left side of the box. This side will be used to label the rows of the box. Label the rows A thru J on the side of the box (the letter I is omitted). Begin with A in the upper left corner of the box and proceed to J in the lower left corner of the box (Figure 3). This labeling should now match that of the serum storage log. The cell in the upper left corner of the box should be cell A1. The lower right cell should be J9. This labeling should be done immediately upon receipt of the serum storage boxes from the repository.

IV. Data Form Completion

For each serum storage box to be shipped, a separate serum storage log must be completed that identifies the ID number of the serum shipped and locates it within the serum storage box. Please note that no more than 6 serum storage boxes may be sent at one time.

The serum storage log contains 81 cells laid out in 9 rows and 9 columns that matches the 9x9 grid of the serum storage box you will be using. The FRONT label on the serum storage box should be oriented to correspond to the FRONT label on the serum storage log. This is done to ensure that the serum location in the box matches its address on the serum log. Check the box to ensure that the grid labeling is on the box and if not, write the grid labeling on the box as specified in the Box Labeling section of this document.

To complete the serum storage log, enter the ID number of the serum specimen and below it the date the serum was collected in the boxes provided (use the labels provided by RTI as much as possible). Be sure that the IDs entered in the cells of the serum storage log match the IDs of the cryotubes in the corresponding cells of the serum storage box.

Once all serum storage logs are completed, the serum shipping form can be completed and the serum storage box numbers can be assigned. To complete the serum shipping form, enter the appropriate center name and

shipping label number in the space provided on the form. The serum shipping label number is a number used to link the individual serum storage boxes with the shipping container they are shipped in. The shipping label number should be placed on the front and top of the shipping container as well as on the serum shipping form. The number is a 4 digit number that is assigned at the clinic. The first digit should be the center number and the last three digits should be a sequential box number (i.e., 1001 is the first shipping container should be labelled number and the last digit is a sequence number from 1 to 6 depending on how many serum storage boxes are sent in the shipment (i.e., 1001-1, 2, 1001-3, ...). One of these labels should go on the top of the serum storage box and the other should go on the front bottom right side of the box itself. A third label should go on the serum samples log to denote the box number. Figure 4 and 5 provide illustrations of the placement of these labels. Once the box numbers are assigned and labels are affixed, enter the date the serum was shipped to the repository and the number of serum storage boxes that were shipped to complete the serum shipping form.

V. Shipping Procedures

A. Shipping Forms

When serum is shipped to the repository, a serum shipping form should be sent along with serum storage logs for each serum storage box shipped. One copy of the serum storage log should be enclosed in its corresponding serum storage box. The original copy of the serum storage logs that are being shipped should be placed in an envelope and taped to the outside of the shipping container along with a copy of the serum shipping form. Keep an additional copy of these forms for your records and send another copy of each of these forms to RTI.

B. Shipping Storage Boxes

It is recommended that you accumulate five or six storage boxes filled with serum before sending a shipment to the repository. Specimen boxes should be wrapped in an absorbent and cushioned material such as a Pampers diaper. This help in conforming to the requirement that there be enough absorbent in the package to handle the entire fluid volume. Then place the wrapped box in a heavy plastic bag that can be heat sealed or made water-tight in some manner.

C. Shipping Container

Dry ice should be placed in the bottom of the shipping container. The wrapped and sealed specimen boxes should then be placed on the dry ice, and more dry ice should be added around the sides of the sealed specimen boxes. Enough cushioning or padding material should be added to prevent drastic shifting as the ice evaporates. On the outside of the shipping container, securely place the following labels:

1. A return address label containing your name, address and phone number.
2. An address label for the repository:

[name]
Repository
Program Resources, Inc.
[name]
[name]
[contact]

Shipments are to be made only on Monday or Tuesday and are to be shipped via Federal Express to ensure quick delivery. Once the serum has been shipped, [name] at the repository should be notified that the shipped is in route. Once the shipment arrives at the repository, he will alert the center that it has arrived.

D. A label stating the following:

MEDICAL MATERIALS
CONFORMS WITH FEDERAL STANDARD
49 CFR 173, 387; 42 CFR 72.25 (C);
AND NIH GUIDE,DATE.....

E. A label stating that BIOMEDICAL MATERIAL is being shipped and who to contact in case of leakage or damage.

Appendix 9

Diagnostic Skin Testing

Tuberculin

Introduction

The major tool in the diagnosis of tuberculosis is the tuberculin skin test. Tuberculin is a biologic product derived from cultures of tubercle bacilli composed largely of tuberculoprotein, the protein of *Mycobacterium tuberculosis*, human or bovine. Tuberculin is not a chemical or synthetic product.

Infection with *M tuberculosis* results in development of skin sensitivity to tuberculin. This occurs when an exposed individual (generally over a long period of time) inhales a droplet aerosol containing the infectious particle, *M tuberculosis*. This individual then may develop a delayed form of hypersensitivity to the tubercle bacillus resulting in a positive Mantoux test which is diagnostic of the infected state.

Infection with *M tuberculosis* results in skin sensitivity to tuberculin. There is an incubation period of six to eight weeks between infection and appearance of this sensitivity. In almost all infected individuals the tuberculin test elicits a measurable reaction. The average size reaction to the Mantoux test is 16 mm. The range forms a normal distribution from 8 mm to 24 mm. Three to 5 percent of the infected population fall outside this distribution.

Technique

The antigen is given in a single dose plastic syringe with a No. 26 or small gauge needle. Even though the material is Tween stabilized to keep it from being adsorbed through the glass, it should not remain in the syringe longer than one hour prior to testing. Intracutaneous injection of 0.1 milliliters PPD is given into the skin of the volar or dorsal aspect of the forearm. After cleaning with alcohol the injection is made with a short, bevelled needle just beneath the surface of the skin. A wheal of from 6 to 10 mm in diameter should be produced. Reading is done in 48 to 72 hours although readings beyond 96 hours are significant if present. A good light and flexible millimeter ruler

should be used. The margins of induration should be found by touch, not sight. The induration is measured in the skin at the point where the needle enters and is usually measured transversely. Recording should be made solely on the basis of size of induration. Erythema should be disregarded and not recorded.

Mumps

Mumps skin test antigen is used to determine the presence of a delayed hypersensitivity reaction. Since most of the population are considered to have had contact or infection with the mumps virus, they usually demonstrate such a reaction if an adequate cellular immune system exists. Therefore, absence of such a reaction suggests presence of anergy.

The Mantoux technique (see above under tuberculin test) is used. An injection of 0.1 ml antigen is given intradermally. Prior to injection the skin is cleansed with an alcohol sponge. The reaction should be examined in 48 to 72 hours (92 hours is permissible). A mean diameter of induration of 5 mm or more is considered positive.

Appendix 10

1987 Revision of Case Definition for AIDS for Surveillance Purposes

For national reporting, a case of AIDS is defined as an illness characterized by one or more of the following "indicator" diseases, depending on the status of laboratory evidence of HIV infection, as shown below.

I. Without Laboratory Evidence of HIV Infection

If laboratory tests for HIV were not performed or gave inconclusive results (see Appendix I) and the patient had no other cause of immunodeficiency listed in Section I.A below, then any disease listed in Section I.B indicates AIDS if it was diagnosed by a definitive method (see Appendix II).

A. Causes of immunodeficiency that disqualify diseases as indicators of AIDS in the absence of laboratory evidence for HIV infection

1. high-dose or long-term systemic corticosteroid therapy or other immunosuppressive/cytotoxic therapy ≤ 3 months before the onset of the indicator disease
2. any of the following diseases diagnosed ≤ 3 months after diagnosis of the indicator disease: Hodgkin's disease, non-Hodgkin's lymphoma (other than primary brain lymphoma), lymphocytic leukemia, multiple myeloma, any other cancer of lymphoreticular or histiocytic tissue, or angioimmunoblastic lymphadenopathy
3. a genetic (congenital) immunodeficiency syndrome or an acquired immunodeficiency syndrome atypical of HIV infection, such as one involving hypogammaglobulinemia

B. Indicator diseases diagnosed definitively

1. candidiasis of the esophagus, trachea, bronchi, or lungs
2. cryptococcosis, extrapulmonary
3. cryptosporidiosis with diarrhea persisting >1 month

4. cytomegalovirus disease of an organ other than liver, spleen, or lymph nodes in a patient >1 month of age
5. herpes simplex virus infection causing a mucocutaneous ulcer that persists longer than 1 month; or bronchitis, pneumonitis, or esophagitis for any duration affecting a patient >1 month of age
6. Kaposi's sarcoma affecting a patient <60 years of age
7. lymphoma of the brain (primary) affecting a patient <60 years of age
8. lymphoid interstitial pneumonia and/or pulmonary lymphoid hyperplasia (LIP/PLH complex) affecting a child <13 years of age
9. Mycobacterium avium complex or M. kansasii disease, disseminated (at a site other than or in addition to lungs, skin, or cervical or hilar lymph nodes)
10. Pneumocystis carinii pneumonia
11. progressive multifocal leukoencephalopathy
12. toxoplasmosis of the brain affecting a patient >1 month of age

II. With Laboratory Evidence for HIV Infection

Regardless of the presence of other causes of immunodeficiency (I.A), in the presence of laboratory evidence of HIV infection (see Appendix I), any disease listed above (I.B) or below (II.A or II.B) indicates a diagnosis of AIDS.

A. Indicator diseases diagnosed definitively

1. bacterial infections, multiple or recurrent (any combination of at least two within a 2-year period), of the following types affecting a child <13 years of age: septicemia, pneumonia, meningitis, bone or joint infection, or abscess of an internal organ or body cavity (excluding otitis media or superficial skin or mucosal abscesses), caused by Haemophilus, Streptococcus (including pneumococcus), or other pyogenic bacteria

2. coccidioidomycosis, disseminated (at a site other than or in addition to lungs or cervical or hilar lymph nodes)
 3. HIV encephalopathy (also called "HIV dementia," "AIDS dementia," or "subacute encephalitis due to HIV") (see Appendix II for description)
 4. histoplasmosis, disseminated (at a site other than or in addition to lungs or cervical or hilar lymph nodes)
 5. isosporiasis with diarrhea persisting >1 month
 6. Kaposi's sarcoma at any age
 7. lymphoma of the brain (primary) at any age
 8. other non-Hodgkin's lymphoma of B-cell or unknown immunologic phenotype and the following histologic types:
 - a. small noncleaved lymphoma (either Burkitt or non-Burkitt type) (see Appendix IV for equivalent terms and numeric codes used in the International Classification of Diseases, Ninth Revision, Clinical Modification)
 - b. immunoblastic sarcoma (equivalent to any of the following, although not necessarily all in combination: immunoblastic lymphoma, large-cell lymphoma, diffuse histiocytic lymphoma, diffuse undifferentiated lymphoma, or high-grade lymphoma) (see Appendix IV for equivalent terms and numeric codes used in the International Classification of Diseases, Ninth Revision, Clinical Modification)
- Note:** Lymphomas are not included here if they are of T-cell immunologic phenotype or their histologic type is not described or is described as "lymphocytic," "lymphoblastic," "small cleaved," or "plasmacytoid lymphocytic"
9. any mycobacterial disease caused by mycobacteria other than M. tuberculosis, disseminated (at a site other than or in addition to lungs, skin, or cervical or hilar lymph nodes)

10. disease caused by M. tuberculosis, extrapulmonary (involving at least one site outside the lungs, regardless of whether there is concurrent pulmonary involvement)
 11. Salmonella (nontyphoid) septicemia, recurrent
 12. HIV wasting syndrome (emaciation, "slim disease") (see Appendix II for description)
- B. Indicator diseases diagnosed presumptively
- Note:** Given the seriousness of diseases indicative of AIDS, it is generally important to diagnose them definitively, especially when therapy that would be used may have serious side effects or when definitive diagnosis is needed for eligibility for antiretroviral therapy. Nonetheless, in some situations, a patient's condition will not permit the performance of definitive tests. In other situations, accepted clinical practice may be to diagnose presumptively based on the presence of characteristic clinical and laboratory abnormalities. Guidelines for presumptive diagnoses are suggested in Appendix III.
1. candidiasis of the esophagus
 2. cytomegalovirus retinitis with loss of vision
 3. Kaposi's sarcoma
 4. lymphoid interstitial pneumonia and/or pulmonary lymphoid hyperplasia (LIP/PLH complex) affecting a child <13 years of age
 5. mycobacterial disease (acid-fast bacilli with species not identified by culture), disseminated (involving at least one site other than or in addition to lungs, skin, or cervical or hilar lymph nodes)
 6. Pneumocystis carinii pneumonia
 7. toxoplasmosis of the brain affecting a patient >1 month of age

III. With Laboratory Evidence Against HIV Infection

With laboratory test results negative for HIV infection (see Appendix I), a diagnosis of AIDS for surveillance purposes is ruled out unless:

- A. all the other causes of immunodeficiency listed above in Section I.A are excluded; AND
- B. the patient has had either:
 - 1. Pneumocystis carinii pneumonia diagnosed by a definitive method (see Appendix II); OR
 - 2. a. any of the other diseases indicative of AIDS listed above in Section I.B diagnosed by a definitive method (see Appendix II); AND
 - b. a T-helper/inducer (CD4) lymphocyte count $<400/\text{mm}^3$.

COMMENTARY

The surveillance of severe disease associated with HIV infection remains an essential, though not the only, indicator of the course of the HIV epidemic. The number of AIDS cases and the relative distribution of cases by demographic, geographic, and behavioral risk variables are the oldest indices of the epidemic, which began in 1981 and for which data are available retrospectively back to 1978. The original surveillance case definition, based on then-available knowledge, provided useful epidemiologic data on severe HIV disease (1). To ensure a reasonable predictive value for underlying immunodeficiency caused by what was then an unknown agent, the indicators of AIDS in the old case definition were restricted to particular opportunistic diseases diagnosed by reliable methods in patients without specific known causes of immunodeficiency. After HIV was discovered to be the cause of AIDS, however, and highly sensitive and specific HIV-antibody tests became available, the spectrum of manifestations of HIV infection became better defined, and classification systems for HIV infection were developed (2-5). It became apparent that some progressive, seriously disabling, and even fatal conditions (e.g., encephalopathy, wasting syndrome) affecting a substantial number of HIV-infected patients were not subject to epidemiologic surveillance, as they were not included in the AIDS case definition. For reporting purposes, the revision adds to the definition most of those severe non-infectious, non-cancerous HIV-associated conditions that are categorized in the CDC clinical classification systems for HIV infection among adults and children (4,5).

Another limitation of the old definition was that AIDS-indicative diseases are diagnosed presumptively (i.e., without confirmation by methods required by the old definition) in 10%-15% of patients diagnosed with such diseases; thus, an appreciable proportion of AIDS cases were missed for reporting purposes (6,7). This proportion may be increasing, which would compromise the old case definition's usefulness as a tool for monitoring trends. The revised case definition permits the reporting of these clinically diagnosed cases as long as there is laboratory evidence of HIV infection.

[figure not shown]
